11.6.4. Safety

Adverse Events
Adverse Events

All AEs reported up to and including the Day 180 visit (Day 195 visit for participants who do not relapse during the study) following enrolment of a participant into the study will be documented for participants in the Safety Population (or Safety OL Population).
 
These will be recorded and coded using the current version of Medical Dictionary for Regulatory Activities (MedDRA). All terms applied will be reviewed by a GSK physician prior to unblinding. If any malaria related coded terms are considered to have lost useful information in the coding step (e.g., if a verbatim term of 'Plasmodium vivax malaria' is mapped to 'malaria'), he/she will recommend a study-specific code, which will be documented. The process will be completed prior to study unblinding.
 
If the grade/intensity is missing for an AE, it will be considered severe/Grade 3 if an AE, or Grade 4 if an SAE and the participant is alive, or Grade 5 if an SAE and the participant dies (i.e. the highest intensity possible) for the summary of AEs by maximum intensity.
 
See Section 11.7.2 for more information on missing and partial dates.
 
Common AEs are those occurring in $\geq 5\%$ of participants in any treatment group.
 
The recurrence of malaria and any associated signs and symptoms are recorded as Disease Related Events (DREs) and will not be classified as AEs.

AE's of Special Interest

AEs of special interest are:
 
 Haematological events AEs with a system organ class (SOC) of "Nervous System Disorders" AEs with a SOC of "Psychiatric Disorders" AEs with a SOC of "Renal and Urinary Disorders" AEs with a SOC of "Hepatobiliary Disorders" 
Haematological events will be identified by GSK physicians, prior to unblinding, from a list of all unique preferred terms observed within the study.

Laboratory Parameters

If a laboratory value which is expected to have a numeric value for summary purposes, has a non-detectable level reported in the database, where the numeric value is missing, but typically a character value starting with '<x' or '>x' is present, the number of decimal places of x will be used to determine how much to add or subtract in order to impute the corresponding numeric value.
 
Example 1: 2 decimal places = '< x' becomes $x - 0.01$
 
Example 2: 1 decimal place = '> x' becomes $x + 0.1$
 
Example 3: 0 decimal places = '< x' becomes $x - 1$
 
Where laboratory assessments were conducted at more than one laboratory, e.g. a single participant may have had their data analysed at different laboratories at different visits, the results will be pooled in the summaries, i.e. all data will be included regardless of the laboratory at which the sample was analysed. A review by the GSK clinical team has shown the normal ranges to be sufficiently similar across the different laboratories, thus pooling of the data is appropriate.

Vital Signs – Mean Arterial Blood Pressure

To be calculated (to 1 decimal place) where systolic and diastolic blood pressure are both present at the same timepoint:

mean arterial blood pressure

$$= \frac{(\textit{systolic blood pressure} + 2(\textit{diastolic blood pressure}))}{3}$$

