Prior to commencing this study, a TQ/ACT interaction study was performed (GSK Study 200951). This drug-drug interaction (DDI) study assessed the safety and pharmacokinetics of TQ when co-administered with DHA-PQP in three parallel groups of n=24 healthy subjects. As expected, PQP-induced prolongation of the QTc interval was observed. Whilst an absolute difference in QTcF elongation was observed between the DHA-PQP alone group and the DHA-PQP plus TQ group, confidence intervals overlapped and the difference was not considered clinically significant. No significant effect of TQ on the PK of DHA or PQP was found. There was a 12% (1 – 26%, 90% CI) increase in the AUC0-inf of TQ when co-administered with DHA-PQP but this is not deemed to be clinically significant, with PK parameters not reaching those previously seen with higher doses that have been tolerated and safely used in other studies. Therefore, no dose adjustments were deemed necessary for co-administration of TQ and DHA-PQP in the present study. No new safety signals were noted in Study 200951 but ECG monitoring will be performed in the present study in accordance with the DHA-PQP label (Eurartesim SmPC).

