	
 
○ GI tolerability – incidence of abdominal pain, heartburn, diarrhoea, constipation, nausea and vomiting.
 
○ Change from baseline in methemoglobin
 
○ Change from baseline in QTcF
 
○ Incidence of protocol-defined SAEs (i.e. a decrease in hemoglobin of <math>\geq 30\%</math> or <math>>3</math> g/dL from baseline; or, a drop in absolute hemoglobin to <math>< 7.0</math>g/dL, in the first 15 days)
 

 
● To evaluate the pharmacokinetics of tafenoquine when co-administered with DHA-PQP in adult subjects with P.vivax malaria.
 
	
 
● Population PK parameters for tafenoquine including but not limited to oral clearance (CL/F) and volume of distribution (V/F).
 

Exploratory	

 
● To explore the genetics of recurrence of P.vivax malaria.
 
	
 
● Incidence of genetically homologous and genetically heterologous P.vivax infections (determined by PCR).
 
● Whole genome sequencing of multiple parasite genes will be undertaken, if parasite count allows (to be reported separately).
 

 
● To examine the relationship between CYP2D6 genotype and risk of P.vivax relapse.
 
	
 
● Percentage of subjects relapsing analyzed according to CYP2D6 genotype.
 

 
● To explore the relationship between the pharmacokinetics of tafenoquine co-administered with DHA-PQP and pharmacodynamic endpoints (if appropriate).
 
	
 
● Population PK (e.g. tafenoquine plasma concentrations) and selected pharmacodynamic (PD) endpoints (e.g., relapse-free efficacy, change in methemoglobin).
 

With regards to the efficacy endpoints, it should be noted that it is not possible to determine if a subject's recurrence of malaria is a relapse or recrudescence. For the purposes of this protocol, the term "relapse" will be used to describe any recurrence of *P.vivax* malaria after clearance of the initial infection. "Recrudescence" applies to the term relating to recurrence for Days 1-14 of the study, where a genetically homologous

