QTcF prolongation	
The product labelling for DHA-PQP (Eurartesim SmPC) notes that in clinical trials, QTc prolongation occurred more frequently and to a larger extent following DHA-PQP than with comparators. Before the 3rd dose, in one of two Phase III studies, 3/767 (0.4%) subjects were reported to have a QTc value >500msec versus none in the comparator group. Absorption of piperazine is increased in the presence of fatty food which may increase its effect on QTc interval.
 
Preclinical studies determined that tafenoquine has a low potential for QTc prolongation. A tafenoquine thorough QT study did not show elongation of the QTcF at clinical doses. In the 200951 DDI study, the greatest increase in QTc was observed 4 hours after the last dose of DHA-PQP in both the DHA-PQP+TQ group and the DHA-PQP alone group; this time point will be a key point of interest for ECGs in this study.
 
The label for primaquine (US prescribing information) notes that primaquine has the potential for QT interval prolongation and advises the need for ECG monitoring in subjects with relevant underlying comorbid conditions, as well as during concomitant administration with QT interval prolonging agents.
	
 
• ECG monitoring will be conducted in this study appropriate to DHA-PQP and primaquine labels. Study treatment stopping criteria are provided for QTc prolongation.
 
• DHA-PQP will be dosed without food.
 

Potential Key Risks of Clinical Significance	Summary of Data/Rationale for Risk	Mitigation Strategy
Study Design		
Risk of relapse in DHA-PQP alone arm	Subjects in the DHA-PQP alone arm are at increased risk of relapse during the study compared to subjects randomized to DHA-PQP+primaquine or DHA-PQP+tafenoquine	
 
• Subjects will be under close observation throughout the study and will receive standard of care treatment at first sign of recurrent malaria (symptomatic or asymptomatic). On site clinic facilities will be available 24 hours a day, 7 days a week to ensure prompt management of any subject who develops recurrent malaria.
 
• At the end of the study, any subject who has not relapsed will be given open label PQ 0.5mg/kg daily for 14 days to minimize the likelihood of relapses after the study.
 

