#### **7.5.1.4 Follow-up of AEs and SAEs**

After the initial AE/SAE report, the investigator is required to proactively follow each subject at subsequent visits/contacts. All SAEs, and non-serious AEs of special interest (as defined in Section [4.6.1](#)) will be followed until resolution, until the condition stabilizes, until the event is otherwise explained, or until the subject is lost to follow-up (as defined in Section [5.4](#)). Further information on follow-up procedures is given in [Appendix 3](#) (Section [12.3](#)).

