#### 9.4.1 Secondary Analyses

For evaluation of the secondary efficacy comparisons, 95% confidence intervals will be provided for the treatment differences of i) DHA-PQP plus TQ versus DHA-PQP plus PQ and ii) DHA-PQP plus PQ versus DHA-PQP alone. An exploratory p-value will also be provided for the DHA-PQP plus PQ versus DHA-PQP alone comparison.

A secondary per protocol analysis will also be performed, excluding subjects who deviate significantly from the protocol. If a subject misses a scheduled study visit from day 28 onwards, they will automatically be excluded from the per protocol population.

Statistical comparisons (i) DHA-PQP plus TQ versus DHA-PQP alone, ii) DHA-PQP plus TQ versus DHA-PQP plus PQ and iii) DHA-PQP plus PQ versus DHA-PQP alone) of secondary efficacy endpoints (relapse-free efficacy at 4 months, time to relapse,

percentage of subjects with recrudescence, parasite clearance time, fever clearance time) will also be performed using survival analysis methodology.

A further sensitivity analysis will be performed in which all subjects will be categorized as either successes or failures at 6 months, analyzed using Exact methods. Subjects taking medication with anti-malarial efficacy during the study will be classified as failures in this analysis.

All safety endpoints will be based on the safety population and presented in tabular and/or graphical format and summarised descriptively according to GSK's Integrated Data Standards Library (IDSL) standards.

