No.	Population	IDSL / Example Shell	Title	Programming Notes	Deliverable
3.27	Safety	LB15	Summary of Worst Case Hematology Results Relative to Normal Range Post-Baseline Relative to Baseline	ICH E3	SAC
3.28	Safety	SAFE_T1	Summary of Haematology Laboratory Data Outside the Reference Range (F3)		SAC
3.29	Safety	SAFE_T2	Summary of Categories of Change from Baseline Haemoglobin (G/L) Data by Time		Headline
3.30	Safety	SAFE_T3	Summary of Haemoglobin Declines Over First 28 Days		SAC
Laboratory: Urinalysis					
3.31	Safety	UR1	Summary of Urinalysis Dipstick Results	IDSL	SAC
Hepatobiliary (Liver)					
3.32	Safety	LIVER1	Summary of Liver Monitoring/Stopping Event Reporting	IDSL	SAC
3.33	Safety	LIVER10	Summary of Hepatobiliary Laboratory Abnormalities	IDSL	SAC
ECG					
3.34	Safety	EG1	Summary of ECG Findings	IDSL	SAC
3.35	Safety	EG2	Summary of Absolute ECG Values by Visit	Include Heart Rate, RR Interval, QRS Duration, Uncorrected QT Interval and QTcF	SAC
3.36	Safety	EG2	Summary of Change from Baseline in ECG Values by Visit	IDSL Include Heart Rate, RR Interval, QRS Duration, Uncorrected QT Interval and QTcF	SAC
3.37	Safety	SAFE_T5	Summary of QTcF Values by Category and Visit		Headline
3.38	Safety	EG11	Summary of Maximum Increase in QTcF Values Post-Baseline Relative to Baseline Category over the First 7 Days		Headline

Safety: Tables					
No.	Population	IDSL / Example Shell	Title	Programming Notes	Deliverable
Vital signs					
3.39	Safety	VS1	Summary of Absolute Values in Vital Signs by Visit	ICH E3 Include Systolic Blood Pressure, Diastolic Blood Pressure, Mean Arterial Blood Pressure, Respiratory Rate and Temperature.	SAC
3.40	Safety	VS1	Summary of Change From Baseline in Vital Signs by Visit	ICH E3 Include Systolic Blood Pressure, Diastolic Blood Pressure, Mean Arterial Blood Pressure, Respiratory Rate and Temperature.	SAC
3.41	Safety	VS3	Summary of Worst Case Vital Sign Results Relative to Normal Range Post-Baseline Relative to Baseline	IDSL	SAC
Methaemoglobin					
3.42	Safety	LB1	Summary of Absolute Values in Methaemoglobin by Visit		SAC
3.43	Safety	LB1	Summary of Change From Baseline in Methaemoglobin by Visit		SAC

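### SAP 11.6.4 leaves QTcF prolongation out of the AEs of special interest without declaring it, and no between-arm estimate of tafenoquine's added QTcF effect is planned

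*SAP*

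**What the plan says.** **AEs of special interest.** Protocol 7.5.1.4 requires follow-up to resolution of all SAEs and of "non-serious AEs of special interest (as defined in Section" 4.6.1). The study-treatment rows of the Section 4.6.1 table are hemolysis in G6PD-deficient subjects, methemoglobinemia and "QTcF prolongation". SAP 11.6.4 opens its list with "AEs of special interest are" and names haematological events and the nervous system, psychiatric, renal/urinary and hepatobiliary classes. SAP 2.1, which records changes from the protocol, does not mention the difference. SAP 8.2 allows safety review team agreements to alter the list, with events identified before unblinding.

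**QTcF as a measurement.** Protocol Section 3 lists "Change from baseline in QTcF" among the key safety endpoints. On the ECG taken 4 hours after the last DHA-PQP dose, Protocol 4.6.1 says "this time point will be a key point of interest for ECGs in this study". The SAP plans ECG findings (Table 3.34), absolute values (3.35), "Summary of Change from Baseline in ECG Values by Visit" (3.36), QTcF categories by visit (3.37, headline) and maximum QTcF increase over the first 7 days (3.38, headline). SAP 11.3.1 gives the 4-hour ECG its own window, 3 to 6 hours after the dose.

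**Method.** Protocol 9.4.1 says safety endpoints will be "presented in tabular and/or graphical format and summarised descriptively".

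**The concern.** There are two separate gaps.

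First, the SAP adds four organ classes that the protocol's risk table does not list and drops one drug risk that it does, without comment. The headline AESI table (3.18) therefore has no place for QT terms, and a reader cannot tell whether that was decided or overlooked.

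Second, the open QT question in this programme is what tafenoquine adds to the piperaquine effect. On the interaction study, Protocol 2.1.4 reports: "Whilst an absolute difference in QTcF elongation was observed between the DHA-PQP alone group and the DHA-PQP plus TQ group". It adds that the confidence intervals overlapped and that the difference was not considered clinically significant; there were 24 healthy subjects per group. This trial has about twice as many per arm, in patients, with a scheduled ECG at the time point the protocol singles out. Per-arm summaries alone would leave readers comparing intervals or category counts by eye once more.

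**Working it through.** **1. The two lists side by side.**

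| Risk or category | Protocol 4.6.1, drug risks | SAP 11.6.4 |
|---|---|---|
| Hemolysis | yes | covered by haematological events |
| Methemoglobinemia | yes | can be covered by haematological events (physician-selected terms) |
| QTcF prolongation | yes | absent |
| Nervous system, psychiatric, renal/urinary, hepatobiliary | no | yes |

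SAP 2.1 does declare that gastrointestinal tolerability will no longer be analysed as an endpoint. The sponsor thus treated a comparable safety change as one to record.

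**2. Would a rare QT event be lost?** One or two events in 50 men is 1/50 = 2% or 2/50 = 4%. Both fall below the 5% cut of Table 3.4 and Figure 3.1. Several headline tables have no such cut: 3.8 and 3.9 (related AEs), 3.12 (double-blind AEs with onset by Study Day 29) and 3.13 (SAEs). Protocol 5.4 requires any case meeting the QT stopping criteria to be reported as an SAE, so it would enter 3.13. Rare QT events would therefore be visible, but not grouped as special interest.

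**3. Why overlapping intervals do not settle the difference.** Suppose each arm's mean has a 95% interval of half-width h. The intervals overlap whenever the means differ by less than 2h. The interval for the difference has half-width √(h² + h²) = 1.41h. A difference between 1.41h and 2h thus excludes zero although the per-arm intervals overlap.

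**4. What category counts can show.** Protocol 4.6.1 cites QTcF above 500 msec in 3/767 = 0.39% (stated as 0.4%). At that rate, the chance of at least one case in an arm of 50 is 1 − (1 − 3/767)^50 = 17.8%. An empty top category is the expected result and says little about a shift in the mean. The cited rate was recorded before the third dose, so it is only a guide to the 4-hour point.

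**5. Precision of a between-arm difference.** Half-width = 1.96 × SD × √(2/n). The n of 50 per arm is from Protocol 9.2.1; 45 allows for its 10% withdrawal. The documents give no SD for QTcF change, so 10 to 25 msec is assumed. At n = 50, √(2/50) = 0.200; at n = 45, √(2/45) = 0.211.

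| Assumed SD (msec) | n = 50 per arm | n = 45 per arm |
|---|---|---|
| 10 | 3.9 | 4.1 |
| 15 | 5.9 | 6.2 |
| 20 | 7.8 | 8.3 |
| 25 | 9.8 | 10.3 |

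These are before baseline adjustment, which would usually narrow them. At the same SD, the half-width is √(24/50) = 0.69 of that available with 24 per group.

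**6. Which Day 3 ECG?** Protocol 7.5.4 schedules two on Day 3: before the last DHA-PQP dose and 4 hours after it. SAP 11.6.1 averages multiple ECGs at the same visit, while SAP 11.3.1 treats the 4-hour reading as a separate time point. The part of shell SAFE_T5 that is shown has one Day 3 block and then continues with dots. Read literally, the averaging rule could blend the 4-hour value with the pre-dose one.

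**The case against.** The strongest reply is that the SAP does what the protocol asks. Protocol 9.4.1 makes safety descriptive, so a missing contrast breaks no commitment. QTcF is measured directly and shown in two headline tables, which is more informative than investigator-reported terms. Protocol 4.6.1 also cites a thorough QT study with no QTcF elongation at clinical doses, and this trial is powered for relapse. Section 4.6.1 is a risk-mitigation table that includes design risks such as relapse and unblinding; 7.5.1.4 invokes it for follow-up of events, not for an analysis. SAP 8.2 leaves the AESI list open.

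Most of this stands, and it rules out three stronger readings that a reader might infer:

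- **That cardiac events in general were dropped.** Section 4.6.1 names QTcF prolongation only. The cardiovascular list in Protocol 12.3.3 governs which CRF pages are completed.
- **That QT is under-analysed or that rare QT events would be hidden.** The five ECG tables, the 4-hour window and the headline AE tables without a cut show otherwise.
- **That the SAP contradicts the protocol by planning no contrast.** It follows the descriptive plan.

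The reply does not remove the two gaps. Section 8.2 permits a correction but neither restores QT nor explains its absence, and 7.5.1.4 does tie the term to 4.6.1. A descriptive plan can include a difference with an interval.

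**Conclusion.** The point holds in a limited form. QTcF prolongation is missing from the SAP's special-interest list although the protocol's cross-reference brings it in, and the change is undeclared. Separately, the SAP text contains no between-arm estimate for a named key safety endpoint at the time point the protocol stresses. The second gap is a limitation of the plan and not an inconsistency between documents. Neither affects the primary analysis.

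The gain available is a 95% interval of roughly ±4 to ±10 msec for tafenoquine's added effect. This rests on an assumed SD of 10 to 25 msec and about 50 men per arm with usable ECGs at baseline and 4 hours. The standard shells EG2 and EG11 (Tables 3.35, 3.36 and 3.38) are not reproduced, so the absence of a contrast is judged from the SAP text, the display list and shell SAFE_T5.

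**What to change.** 1. In SAP 11.6.4, add a QT-prolongation category with its preferred terms fixed before unblinding, and show it in Table 3.18. Alternatively, state and justify the omission in SAP 2.1.
2. Alongside Table 3.36, add the baseline-adjusted (ANCOVA) difference in QTcF change, TQ+DHA-PQP minus DHA-PQP only, with 95% CI, at 4 hours after the last DHA-PQP dose. Label it descriptive, with no formal test.
3. State that this value uses only the 4-hour window of SAP 11.3.1 and is not averaged with the Day 3 pre-dose ECG under 11.6.1.

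The cost is a few lines of SAP wording, one group of rows in Table 3.18 and one model. All the data are already collected; sample size and alpha are unaffected. The downside is one further estimate that must be read as descriptive.

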11.7. Appendix 7: Reporting Standards for Missing Data

11.7.1. Premature Withdrawals

Element	Reporting Detail
General	
A participant is considered to have completed the double-blind study if they are randomized to blinded study treatment and complete the Day 180 visit.
 
A participant is considered to have completed the open-label PQ phase of the study if they are included in the safety OL population and complete the Day 195 visit.
 
Withdrawn participants will not be replaced in the study.
 
All available data from participants who were withdrawn from the study will be listed and all available planned data will be included in summary tables and figures, unless otherwise specified.

11.7.2. Handling of Missing Data

Element	Reporting Detail
General	
Missing data occurs when any requested data is not provided, leading to blank fields on the collection instrument:
 
These data will be indicated by the use of a “blank” in participant listing displays. Unless all data for a specific visit are missing in which case the data is excluded from the table.
 
Answers such as “Not applicable” and “Not evaluable” are not considered to be missing data and should be displayed as such.

Outliers	
Any participants with outlying results may be excluded in additional ad hoc summaries and/or statistical analyses. These will be documented along with the reason for exclusion in the clinical study report, but the primary conclusions will remain based on the full population sets.

11.7.2.1. Handling of Missing and Partial Dates

Element	Reporting Detail
General	
Partial dates will be displayed as captured in participant listing displays.

Adverse Events	
It is not possible to record partial dates in the eCRF for AEs.
 
Completely missing start or end dates will remain missing, with no imputation applied. Consequently, time to onset and duration of such events will be missing.
 
AEs with entirely missing start dates will be assumed to have started during the double-blind treatment phase for reporting. AEs where the start date is equal to that of blinded study medication, but where the start time is unknown will be assumed to have started during the double-blind treatment phase. AEs with an onset date on or after that of DHA-PQP administration, and where blinded medication was taken on a later date, will be considered to have started during the DHA-PQP phase.
 
AEs with missing end dates and/or times are not anticipated to affect reporting

Element	Reporting Detail
	(with the exception that duration will be missing in the listings of AEs).
Concomitant medications / Medical History	
Missing Dates
 
Where the start or stop date of a concomitant medication record is entirely unknown and is totally missing at the time of reporting, the eCRF flags 'Taken prior to study?' and 'Ongoing medication?' will be used in order to derive whether it is prior or concurrent.
 
If these flags are also missing, then it will be assumed that it is concurrent.
 
In the event that use of the same medication is recorded at more than one visit (and if this has not been collapsed to one record), the eCRF flags will be cross-checked for both records.
 
Partial Dates
 
Partial dates for any concomitant medications recorded in the CRF will be imputed using the following convention:
 
If the partial date is a start date, a '01' will be used for the day and 'Jan' will be used for the month
 
If the partial date is a stop date, a '28/29/30/31' will be used for the day (dependent on the month and year) and 'Dec' will be used for the month.
 
The recorded partial date will be displayed in listings.

